### **9.2.2. Adverse Event Summaries**

An overall summary of AEs by treatment group will include the following:

- Number (%) of participants reporting any TEAEs
- Number (%) of participants reporting any serious TEAEs
- Number (%) of participants reporting any Grade 3 or higher TEAEs
- Number (%) of participants reporting any treatment-related TEAEs
- Number (%) of participants who temporarily interrupted study drug because of TEAEs
- Number (%) of participants who permanently discontinued study drug because of TEAEs
- Number (%) of participants who had a fatal TEAE

The following summaries will be produced by MedDRA term (if 2 or fewer participants appear in a table, a listing may be appropriate):

- Summary of TEAEs by SOC and PT
- Summary of TEAEs by PT in decreasing order of frequency
- Summary of Grade 3 or higher TEAEs by SOC and PT
- Summary of Grade 3 or higher TEAEs by PT in decreasing order of frequency
- Summary of serious TEAEs by SOC and PT
- Summary of serious TEAEs by PT in decreasing order of frequency

- Summary of treatment-related TEAEs by SOC and PT
- Summary of treatment-related TEAEs by PT in decreasing order of frequency
- Summary of Grade 3 or higher treatment-related TEAEs by SOC and PT
- Summary of treatment-related serious TEAEs by SOC and PT
- Summary of TEAEs leading to temporarily interrupted study drug
- Summary of TEAEs with a fatal outcome by SOC and PT
- Summary of TEAEs leading to interruption of study drug by SOC and PT
- Summary of TEAEs leading to discontinuation of study drug by SOC and PT

Subgroup analysis for TEAEs by age, sex, ethnicity, and region will also be provided.

Adverse events of interest will be summarized in the following categories:

- Cytopenias
  - Anemia
  - Thrombocytopenia
  - Neutropenia
- Herpes zoster
- Viral skin infections
- Nonmelanoma skin neoplasms
- Liver function test elevations
- Malignancies
- Major adverse cardiovascular events
- Venous and arterial thromboembolic events
- Thrombocytosis and elevated mean platelet volume

### **9.3. Clinical Laboratory Tests**

#### **9.3.1. Laboratory Value Definitions**

All laboratory assessments will be performed using a central laboratory except for urine pregnancy tests (as applicable). Laboratory values and change from baseline values will be summarized descriptively by visit, and non-numeric test values will be tabulated when necessary.

The baseline value will be determined using the last nonmissing value collected before the first application, prioritizing scheduled assessments for baseline identification over unscheduled visits if they were on the same date. The last record before administration with the highest priority will be considered the baseline record. For baseline laboratory candidates with the same date and time in the same priority category, additional rules may be provided after consultation with the medical monitor to delineate which value will be defined as baseline.

### 9.3.2. Laboratory Value Summaries

Clinical laboratory tests, including hematology and serum chemistry, will be performed at the Protocol-specified visits. If specific safety issues arise, additional unscheduled laboratory tests/analyses may be performed at the discretion of the investigator.

All test results and associated normal ranges from central laboratories will be reported in SI units. All tests with numerical values will have a unique unit per test. Any laboratory test results and associated normal ranges from local laboratories will be converted to SI units.

When there are multiple nonmissing laboratory values for a participant's particular test at a scheduled visit, central laboratory values have higher priority over local laboratory values. If a tie still exists, the laboratory value with the smallest laboratory sequence number will be used in by-visit summaries.

For test results that will be summarized with available normal ranges, the number and percentage of participants with the laboratory values being low (but never high), normal, high (but never low), and both low and high will be calculated for each test. This shift summary will be produced for each test for the safety population in the VC and VCE period. Shift tables will be presented showing change in CTCAE grade from baseline to worst grade postbaseline as well. The denominator for the percentage calculation will use the number of participants in the baseline category.

### 9.4. Vital Signs

Values at each scheduled visit, change, and percentage change from baseline for vital signs, including systolic blood pressure, diastolic blood pressure, pulse, respiratory rate, and body temperature, will be summarized descriptively.

Criteria for clinically notable vital sign abnormalities are defined in [Table 5](#). The abnormal values for participants exhibiting clinically notable vital sign abnormalities will be listed along with their assigned treatment group. Alert vital signs are defined as an absolute value outside the defined range and percentage change from baseline > 25%. The abnormal values for participants exhibiting alert vital sign abnormalities will be listed.

**Table 5: Criteria for Clinically Notable Vital Sign Abnormalities**

Parameter	High Threshold	Low Threshold
Systolic blood pressure	> 155 mm Hg	< 85 mm Hg
Diastolic blood pressure	> 100 mm Hg	< 40 mm Hg
Pulse	> 100 bpm	< 45 bpm
Temperature	> 38.0°C	< 35.5°C
Respiratory rate	> 20 breaths/min	< 8 breaths/min

## **10. INTERIM ANALYSES**

No formal interim analysis is planned for this study. There are 2 formal planned analyses:

- The primary analysis will occur after the primary database lock, when all participants have completed the VC period (ie, up to Week 8). The sponsor will be unblinded after the primary database lock; however, investigators and participants will remain blinded to the individual study treatment assignment.
- The final analysis will occur when all participants have completed or withdrawn from the study.

## 11. CHANGES AND MODIFICATIONS TO THE ANALYSIS PLAN

All versions of the SAP are listed in [Table 6](#).

**Table 6: Statistical Analysis Plan Versions**

SAP Version	Date
Original	06 MAY 2025

### 11.1. Changes to Protocol-Defined Analyses

All endpoints in Section 2.2 have been rephrased from the Protocol in a manner that is consistent with estimand guidance. The rephrasing is a change in presentation only and does not alter the interpretation or intended analyses of these endpoints from the Protocol.

The definition of VCE primary population and VCE escape population in Sections 5.3.5 and 5.3.6 has been modified in a more accurate language.

### 11.2. Changes to the Statistical Analysis Plan

Not applicable.

## APPENDIX A. PLANNED TABLES, FIGURES, AND LISTINGS

This appendix provides a list of the planned tables, figures, and listing for the clinical study report. Standard tables will follow the conventions in the Standard Safety Tables initial version. Shells are provided for nonstandard tables. In-text tables are identical in structure and content as appendix tables but follow a Rich Text Format.

The list of tables, figures, listings, and the shells are to be used as a guideline. Modifications of the list or shells that do not otherwise affect the nature of the analysis will not warrant an amendment to the SAP.

### Tables

Table No.	Title	Population	Standard
Baseline Demographic and Characteristic			
1.1.1	Analysis Populations	All	X
1.1.2.1	Summary of Participant Disposition in the VC Period	ITT	X
1.1.2.2	Summary of Participant Disposition in the VCE Period	VCE Primary	X
1.1.2.3	Summary of Participant Disposition in the Escape Arm	VCE Escape	X
1.1.3	Summary of Number of Participants Enrolled by Country and Site	ITT	X
1.1.4.1	Summary of Protocol Deviations	ITT	X
1.1.4.2	Summary of Protocol Deviations	VCE Primary	X
1.1.4.3	Summary of Protocol Deviations	VCE Escape	X
1.2.1	Summary of Demographics and Baseline Characteristics	ITT	X
1.2.2	Summary of Demographics and Baseline Characteristics	VCE Primary	X
1.2.3	Summary of Demographics and Baseline Characteristics	VCE Escape	X
1.3.1	Summary of Baseline Disease Characteristics	ITT	X
1.3.2	Summary of Baseline Disease Characteristics	VCE Primary	X
1.3.3	Summary of Baseline Disease Characteristics	VCE Escape	X
1.4.1	Summary of Prior Medications	ITT	X
1.4.2.1	Summary of Prior Medications for Atopic Dermatitis	ITT	X
1.4.2.2	Summary of Prior Medications for Atopic Dermatitis by Therapy Type and Discontinuation Reason	ITT	X
1.4.3.1	Summary of Concomitant Medications During the VC Period	ITT	X
1.4.3.2	Summary of Concomitant Medications During the VCE Period	VCE Primary	X
1.4.3.3	Summary of Concomitant Medications During the Escape Arm	VCE Escape	X
1.4.3.4	Summary of Concomitant Medications for AD During the VC Period	ITT	X
1.4.3.5	Summary of Concomitant Medications for AD During the VCE Period	VCE Primary	X
1.4.3.6	Summary of Concomitant Medications for AD During the Escape Arm	VCE Escape	X
1.5	Summary of General Medical History	ITT	X
Efficacy			
IGA			
2.1.1	Summary and Analysis of Participants Achieving IGA-TS in the DB Treatment Period	ITT	
2.1.2	Summary and Sensitivity Analysis of Participants Achieving IGA-TS at Week 8 by Multiple Imputations	ITT	
2.1.3	Summary and Analysis of Participants Achieving IGA-TS in the VC Period	PP	
2.1.4	Summary and Analysis of Participants Achieving IGA-TS by Baseline EASI Score ( $< 16$ or $\geq 16$ ) in the DB Treatment Period	ITT	
2.1.5	Summary and Analysis of Participants Achieving IGA-TS by Age in the DB Treatment Period	ITT	

Table No.	Title	Population	Standard
2.1.6	Summary and Analysis of Participants Achieving IGA-TS by Sex in the DB Treatment Period	ITT	
2.1.7	Summary and Analysis of Participants Achieving IGA-TS by Race in the DB Treatment Period	ITT	
2.1.8	Summary and Analysis of Participants Achieving IGA-TS by Region (ROW or Europe) in the DB Treatment Period	ITT	
2.1.9	Summary and Analysis of Participants Achieving IGA-TS by Prior Systemic or Phototherapy in the DB Treatment Period	ITT	
2.1.10	Summary and Analysis of Participants Achieving IGA-TS by Season Enrolled in the DB Treatment Period	ITT	
2.1.11.1	Summary and Analysis of Participants Achieving an IGA Score of 0 or 1 in the DB Treatment Period	ITT	
2.1.12.1	Summary of Participants in Each Category of IGA Score in the DB Treatment Period	ITT	
2.1.13.1	Summary of Participants Achieving IGA-TS in the Escape Arm	VCE Escape (Entered escape arm at Week 8)	
EASI			
2.2.1	Summary and Analysis of Participants Achieving EASI75 in the DB Treatment Period	ITT	
2.2.2	Summary and Sensitivity Analysis of Participant Achieving EASI75 at Week 8 by Multiple Imputations	ITT	
2.2.3	Summary and Analysis of Participants Achieving EASI75 in the VC Period	PP	
2.2.4	Summary and Analysis of Participants Achieving EASI75 by Baseline EASI Score in the DB Treatment Period	ITT	
2.2.5	Summary and Analysis of Participants Achieving EASI75 by Age in the Blinded Treatment Period	ITT	
2.2.6	Summary and Analysis of Participants Achieving EASI75 by Sex in the DB Treatment Period	ITT	
2.2.7	Summary and Analysis of Participants Achieving EASI75 by Race in the DB Treatment Period	ITT	
2.2.8	Summary and Analysis of Participants Achieving EASI75 by Region (ROW or Europe) in the DB Treatment Period	ITT	
2.2.9	Summary and Analysis of Participants Achieving EASI75 by Prior Systemic or Phototherapy in the DB Treatment Period	ITT	
2.2.10	Summary and Analysis of Participants Achieving EASI75 by Season Enrolled in the DB Treatment Period	ITT	
2.2.11	Summary and Analysis of Participants Achieving EASI50 in the DB Treatment Period	ITT	
2.2.12	Summary and Analysis of Participants Achieving EASI90 in the DB Treatment Period	ITT	
2.2.13.1	Summary and Analysis of By-Visit EASI Score in the DB Treatment Period	ITT	
2.2.14.1	Summary of Participants in Each Category of EASI Score in the DB Treatment Period	ITT	
2.2.15	Summary and Analysis of Participants achieving both EASI 75 and IGA-TS in the DB Treatment Period	ITT	
2.2.16	Summary and Analysis of Time to Open-Label Escape Arm	Participants who entered VCE period	
2.2.17.1	Summary and Analysis of Time to concurrently having IGA Score $\geq 3$ , EASI Score $\geq 16$ , Itch NRS Score $\geq 4$ , BSA $\geq 10\%$ , and DLQI Score $> 10$	ITT	

Table No.	Title	Population	Standard
2.2.17.2	Summary of Participants concurrently having IGA Score $\geq 3$ , EASI Score $\geq 16$ , Itch NRS Score $\geq 4$ , BSA $\geq 10\%$ , and DLQI Score $> 10$ in the DB Treatment Period	ITT	
2.2.18	Summary of Participants Achieving EASI75 in the Escape Arm	VCE Escape (Entered escape arm at Week 8)	
Itch NRS Score			
2.3.1	Summary and Analysis of Participants Achieving $\geq 4$ -Point Improvement in Itch NRS Score in the VC Period	ITT	
2.3.2	Summary and Analysis of Participants with ITCH4 From Baseline to Day 7 in the VC Period	ITT	
2.3.3	Summary and Analysis of Participants With ITCH4 From Baseline to Day 3 in the VC Period	ITT	
2.3.4	Summary and Analysis of Participants With ITCH4 From Baseline to Day 2 in the VC Period	ITT	
2.3.5.1	Summary and Analysis of By-Visit Itch NRS Score in the VC Period	ITT	
2.3.5.2	Summary of By-Visit Itch NRS Score in the VCE DB Treatment Period	VCE Primary	
2.3.6	Summary and Analysis of Time to $\geq 2$ -Point Improvement in Itch NRS Score in the VC Period	ITT	
2.3.7	Summary and Analysis of Time to $\geq 4$ -Point Improvement in Itch NRS Score in the VC Period	ITT	
2.3.8	Summary and Analysis of Daily Itch NRS Score in the VC Period	ITT	X
SCORAD			
2.4.1.1	Summary and Analysis of By-Visit SCORAD Total Score in the DB Treatment Period	ITT	
Current Itch NRS			
2.5.1	Summary and Analysis of By-timepoint Current Itch on Day 1	ITT	
2.5.2	Summary and Analysis of Participants Achieving $\geq 2$ -Point Improvement in Current Itch NRS Score on Day 1	ITT	
2.5.3	Summary and Analysis of Participants Achieving $\geq 4$ -Point Improvement in Current Itch NRS Score on Day 1	ITT	
Skin Pain NRS Score			
2.6.1.1	Summary and Analysis of By-Visit Skin Pain NRS Score in the VC Period	ITT	
2.6.1.2	Summary and Analysis of By-Visit Pain NRS Score in the VCE DB Treatment Period	VCE Primary	
2.6.2	Summary and Analysis of Daily Skin Pain NRS Score in the VC Period	ITT	X
DLQI			
2.7.1	Summary and Analysis of By-Visit Total DLQI Score in the DB Treatment Period	ITT	
2.7.3	Summary and Analysis of Participants Achieving $\geq 4$ -Point Improvement in DLQI From Baseline in the DB Treatment Period	ITT	
Patient-Oriented Eczema Measure			
2.8.1	Summary and Analysis of By-Visit Total POEM Score in the DB Treatment Period	ITT	
2.8.3	Summary of Participants in Each Category of POEM Score in the DB Treatment Period	ITT	
EQ-5D-5L			
2.9.1	Summary and Analysis of By-Visit EQ-5D-5L VAS Score in the DB Treatment Period	ITT	
2.9.3	Summary of Participants in Each Category of EQ-5D-5L Score in the DB Treatment Period	ITT	

Table No.	Title	Population	Standard
WPAI-AD			
2.10.1	Summary and Analysis of By-Visit WPAI-AD Score in the DB Treatment Period	ITT	
PROMIS			
2.11.1	Summary and Analysis of By-Visit PROMIS Short Form- Sleep-Related Impairment 8a Score in the DB Treatment Period	ITT	
2.11.3	Summary and Analysis of By-Visit PROMIS Short Form- Sleep Disturbance 8b Score in the DB Treatment Period	ITT	
HADS			
2.12.1	Summary and Analysis of By-Visit HADS Score in the DB Treatment Period	ITT	
BSA			
2.13.1	Summary and Analysis of Total %BSA Affected by AD in the DB Treatment Period	ITT	
2.13.3	Summary of By-Visit Change From Baseline in the Number of Intertriginous Regions With Active AD Involvement in the DB Treatment Period	ITT	
Desensitization and Rebound in the VCE DB Period			
2.14.1	Summary and Analysis of Participants Experiencing a Relapse After Study Treatment Discontinuation	Study completers who achieved EASI75 at Week 24 and entered safety follow-up	
2.14.2	Summary and Analysis of Participants' By-Visit Time Off Study Treatment Due to Lesion Clearance During VCE Period	VCE Primary	
2.14.3	Summary and Analysis of Participants' By-Visit Time on Study Treatment During the VCE Period	VCE Primary	
2.14.4	Summary and Analysis of Time to First Re-Treatment During the VCE Period	VCE Re-Treatment evaluable	
Safety			
Exposure			
3.1.1.X	Summary of Exposure During the VC Period	Safety	X
3.1.2	Summary of Exposure (Baseline to Week 24)	Safety	X
3.1.3	Summary of Study Drug Compliance During the VC Period	Safety	X
Adverse Events			
3.2.1.1.X	Overall Summary of Treatment-Emergent Adverse Events in the VC Period	Safety	X
3.2.1.2	Overall Summary of Treatment-Emergent Adverse Events for Participants Who Applied Ruxolitinib Cream Throughout the Study (Baseline to Week 24)	Safety	X
3.2.1.3	Overall Summary of Exposure-Adjusted Treatment-Emergent Adverse Events (Baseline to Week 24)	Safety	X
3.2.2.1.X	Summary of Treatment-Emergent Adverse Events by MedDRA System Organ Class and Preferred Term in the VC Period	Safety	X
3.2.2.2	Summary of Treatment-Emergent Adverse Events by MedDRA System Organ Class and Preferred Term for Participants Who Applied Ruxolitinib Cream Throughout the Study (Baseline to Week 24)	Safety	X
3.2.3.1.X	Summary of Treatment-Emergent Adverse Events by MedDRA Preferred Term in Decreasing Order of Frequency in the VC Period	Safety	X
3.2.3.2	Summary of Treatment-Emergent Adverse Events by MedDRA Preferred Term in Decreasing Order of Frequency for Participants Who Applied Ruxolitinib Cream Throughout the Study (Baseline to Week 24)	Safety	X

Table No.	Title	Population	Standard
3.2.3.3	Summary of Exposure-Adjusted Incidence Rates of Treatment-Emergent Adverse Events by MedDRA Preferred Term in Decreasing Order of Frequency (Baseline to Week 24)	Safety	X
3.2.3.4.X	Summary of Application Site Reactions by MedDRA Preferred Term in Decreasing Order of Frequency in the VC Period	Safety	X
3.2.3.5	Summary of Application Site Reactions by MedDRA Preferred Term in Decreasing Order of Frequency for Participants Who Applied Ruxolitinib Cream Throughout the Study (Baseline to Week 24)	Safety	X
3.2.3.6	Summary of Exposure-Adjusted Incidence Rates of Application Site Reactions by MedDRA Preferred Term in Decreasing Order of Frequency (Baseline to Week 24)	Safety	X
3.2.4.1.X	Summary of Grade 3 or Higher Treatment-Emergent Adverse Events by MedDRA System Organ Class and Preferred Term in the VC Period	Safety	X
3.2.4.2	Summary of Grade 3 or Higher Treatment-Emergent Adverse Events by MedDRA System Organ Class and Preferred Term for Participants Who Applied Ruxolitinib Cream Throughout the Study (Baseline to Week 24)	Safety	X
3.2.5.1.X	Summary of Grade 3 or Higher Treatment-Emergent Adverse Events by MedDRA Preferred Term in Decreasing Order of Frequency in the VC Period	Safety	X
3.2.5.2	Summary of Grade 3 or Higher Treatment-Emergent Adverse Events by MedDRA Preferred Term in Decreasing Order of Frequency for Participants Who Applied Ruxolitinib Cream Throughout the Study (Baseline to Week 24)	Safety	X
3.2.6.1.X	Summary of Serious Treatment-Emergent Adverse Events by MedDRA System Organ Class and Preferred Term	Safety	X
3.2.6.2	Summary of Serious Treatment-Emergent Adverse Events by MedDRA System Organ Class and Preferred Term for Participants Who Applied Ruxolitinib Cream Throughout the Study (Baseline to Week 24)	Safety	X
3.2.7.1.X	Summary of Serious Treatment-Emergent Adverse Events by MedDRA Preferred Term in Decreasing Order of Frequency in the VC Period	Safety	X
3.2.7.2	Summary of Serious Treatment-Emergent Adverse Events by MedDRA Preferred Term in Decreasing Order of Frequency for Participants Who Applied Ruxolitinib Cream Throughout the Study (Baseline to Week 24)	Safety	X
3.2.8.1.X	Summary of Treatment-Related Treatment-Emergent Adverse Events by MedDRA System Organ Class and Preferred Term in the VC Period	Safety	X
3.2.8.2	Summary of Treatment-Related Treatment-Emergent Adverse Events by MedDRA System Organ Class and Preferred Term for Participants Who Applied Ruxolitinib Cream Throughout the Study (Baseline to Week 24)	Safety	X
3.2.9.1.X	Summary of Treatment-Related Treatment-Emergent Adverse Events by MedDRA Preferred Term in Decreasing Order of Frequency in the VC Period	Safety	X
3.2.9.2	Summary of Treatment-Related Treatment-Emergent Adverse Events by MedDRA Preferred Term in Decreasing Order of Frequency for Participants Who Applied Ruxolitinib Cream Throughout the Study (Baseline to Week 24)	Safety	X
3.2.10.1.X	Summary of Grade 3 or Higher Treatment-Related Treatment-Emergent Adverse Events by MedDRA System Organ Class and Preferred Term in the VC Period	Safety	X
3.2.10.2	Summary of Grade 3 or Higher Treatment-Related Treatment-Emergent Adverse Events by MedDRA System Organ Class and Preferred Term for Participants Who Applied Ruxolitinib Cream Throughout the Study (Baseline to Week 24)	Safety	X
3.2.11.1.X	Summary of Treatment-Related Serious Treatment-Emergent Adverse Events by MedDRA System Organ Class and Preferred Term in the VC Period	Safety	X

Table No.	Title	Population	Standard
3.2.11.2	Summary of Treatment-Related Serious Treatment-Emergent Adverse Events by MedDRA System Organ Class and Preferred Term for Participants Who Applied Ruxolitinib Cream Throughout the Study (Baseline to Week 24)	Safety	X
3.2.12.1.X	Summary of Treatment-Emergent Adverse Events With a Fatal Outcome by MedDRA System Organ Class and Preferred Term in the VC Period	Safety	X
3.2.12.2	Summary of Treatment-Emergent Adverse Events With a Fatal Outcome by MedDRA System Organ Class and Preferred Term for Participants Who Applied Ruxolitinib Cream Throughout the Study (Baseline to Week 24)	Safety	X
3.2.13.1.X	Summary of Treatment-Emergent Adverse Events Leading to Dose Interruption by MedDRA System Organ Class and Preferred Term in the VC Period	Safety	X
3.2.13.2	Summary of Treatment-Emergent Adverse Events Leading to Dose Interruption by MedDRA System Organ Class and Preferred Term for Participants who Applied Ruxolitinib Cream Throughout the Study (Baseline to Week 24)	Safety	X
3.2.14.1.X	Summary of Treatment-Emergent Adverse Events Leading to Discontinuation of Study Drug by MedDRA System Organ Class and Preferred Term in the VC Period	Safety	X
3.2.14.2	Summary of Treatment-Emergent Adverse Events Leading to Discontinuation of Study Drug by MedDRA System Organ Class and Preferred Term for Participants Who Applied Ruxolitinib Cream Throughout the Study (Baseline to Week 24)	Safety	X
3.2.15.X	Summary of Treatment-Emergent Adverse Events of Interest by MedDRA System Organ Class and Preferred Term in the VC period	Safety	X
3.2.16.X	Summary of Treatment-Emergent Adverse Events of Interest by MedDRA Preferred Term in Decreasing Order of Frequency in the VC period	Safety	X
Laboratory			
3.3.1.X	Summary of Laboratory Values – Hematology in the VC Period	Safety	X
3.3.2.X	Summary of Laboratory Values – Chemistry in the VC Period	Safety	X
3.3.3.X	Shift Summary of Hematology Laboratory Values in CTCAE Grade – To the Worst Abnormal Value in the VC Period	Safety	X
3.3.4.X	Shift Summary of Chemistry Laboratory Values in CTCAE Grade – To the Worst Abnormal Value in the VC Period	Safety	X
3.3.5.X	Shift Summary of Hematology Values – To the Worst Abnormal Value in the VC Period	Safety	X
3.3.6.X	Shift Summary of Chemistry Values – To the Worst Abnormal Value in the VC Period	Safety	X
Vital Signs			
3.5.1.X	Summary of Systolic Blood Pressure in the VC Period	Safety	X
3.5.2.X	Summary of Diastolic Blood Pressure in the VC Period	Safety	X
3.5.3.X	Summary of Pulse in the VC Period	Safety	X
3.5.4.X	Summary of Respiratory Rate in the VC Period	Safety	X
3.5.5.X	Summary of Body Temperature in the VC Period	Safety	X

Note: Safety table that ends with X will be repeated for VCE primary population in the VCE DB period, and VCE escape population in the escape arm.

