8.2.2.1. Characterization of Atopic Dermatitis Involvement in Intertriginous Regions

The presence of AD lesions in the intertriginous regions (ie, axillae, anogenital area, inframammary folds, and infra-abdominal folds) will be determined at each visit and documented in the eCRF (see [Table 3](#) and [Table 4](#)).

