10.4. Statistical Analyses

10.4.1. Primary Analysis

The primary analysis will be based on the ITT population. The primary alternative hypothesis (superiority of ruxolitinib 1.5% cream BID compared with vehicle cream BID) will be tested using a CMH test stratified by baseline EASI score and geographic region. The p-values and overall odds ratio with 95% CI between the ruxolitinib 1.5% cream BID and vehicle cream BID treatment groups will be provided. The p-values will be compared with the 2-sided α level of 0.05. A summary of EASI75 and IGA-TS rates will be reported for each treatment group. Stratum-adjusted rate differences (ruxolitinib 1.5% cream BID vs vehicle cream BID) on EASI75 and IGA-TS and the 95% CI will be computed using Mantel-Haenszel weights ([Mantel and Haenszel 1959](#)).

Participants with missing Week 8 scores for any reason will be defined as nonresponders for the primary analysis. Similar analyses will also be performed in the PP population for the coprimary endpoints. A longitudinal logistic regression with repeated measurements will be performed as a sensitivity analysis. In addition, other missing data imputation methods including multiple imputation and tipping point analysis may be conducted to examine the potential effects of missing data. Subgroup analysis by baseline characteristic (eg, geographic region, age, gender, race, baseline EASI score, season the participant was enrolled, prior cyclosporine therapy, and intertriginous involvement at baseline) will be performed. Details will be provided in the SAP.

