## **5.3. Analysis Populations**

### **5.3.1. Intent-to-Treat Population**

All participants who are randomized to the study constitute the ITT population. Treatment groups for this population will be defined according to the treatment assignment at the time of randomization regardless of the actual study treatment the participant might apply during their participation in the study.

The ITT population will be used for the summary of all efficacy data in the VC and VCE DB periods.

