#### **6.1.2. Baseline Disease Characteristics**

Baseline disease characteristics summarized for the ITT population, the VCE primary population, and the VCE escape population include but are not limited to the following:

- Time since first onset of AD
- Prior history of asthma (no/yes)
- Prior allergies (food, environmental) (no/yes)
- History of contact dermatitis (no/yes)
- Common complications of AD
- Time since onset of current AD episode
- Facial and/or neck involvement (no/yes) during past episodes
- Number of AD episodes/flare-ups over the last 12 months
- Average duration of episodes/flare-ups over the last 12 months
- Baseline EASI score
- Baseline %BSA
- Baseline DLQI score
- Baseline Itch NRS score

- Baseline Skin Pain NRS score
- Inadequate response to TCS (no/yes)
- If inadequate response to TCS is no, prior systemic therapy over the last 12 months (no/yes)
- If inadequate response to TCS is no, prior phototherapy over the last 12 months (no/yes)
- Intolerance to TCS (no/yes)
- Contraindication to TCS (no/yes)
- Inadequate response to TCI (no/yes); if inadequate response to TCI is no, prior systemic therapy over the last 12 months (no/yes)
- If inadequate response to TCI is no, prior phototherapy over the last 12 months (no/yes)
- Intolerance to TCI (no/yes)
- Contraindication to TCI (no/yes)
- Prior systemic therapy (no/yes) over the last 12 months
- Prior phototherapy (no/yes) over the last 12 months
- Intertriginous involvement at baseline (no/yes)

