### 7.3.3. Subgroup Analyses for the Coprimary Endpoints

Subgroup analysis will be performed for the coprimary endpoints based on the following participant demographics and baseline disease characteristics variables for those participants whose data are available:

- Baseline EASI score ( $\geq 16$ ,  $< 16$ )
- Age (18 to  $< 65$  years,  $\geq 65$  years)
- Sex (male, female)
- Race
- Geographic region (Europe vs ROW)
- Prior systemic or phototherapy (yes or no)
- Season the participant was enrolled

Season the participant was enrolled will be defined as below:

- Spring: March to May (Northern Hemisphere) and September to November (Southern Hemisphere).
- Summer: June to August (Northern Hemisphere) and December to February (Southern Hemisphere).
- Fall: September to November (Northern Hemisphere) and March to May (Southern Hemisphere).
- Winter: December to February (Northern Hemisphere) and June to August (Southern Hemisphere).

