4.12.1	Mean and Standard Error Plot of By-Visit HADS Score	ITT
4.12.2	Mean and Standard Error Plot of By-Visit Change From Baseline in HADS Score	ITT
BSA		
4.13.1	Mean and Standard Error Plot of By-Visit Total %BSA Affected by AD	ITT
4.13.2	Mean and Standard Error Plot of By-Visit Change From Baseline in Total %BSA Affected by AD	ITT
4.13.3	Mean and Standard Error Plot of By-Visit Change From Baseline in the Number of Intertriginous Regions With Active AD Involvement	ITT
Laboratory		
4.14.1.X	Box Plot of Selected Hematology Results by Visit in the VC Period	Safety
4.14.2.X	Box Plot of change from baseline in Selected Hematology Results by Visit in the VC Period	Safety
4.14.3.X	Box Plot of Percentage Change from Baseline in Selected Hematology Results by Visit in the VC Period	Safety
Vital Signs		
4.15.1.X	Box Plot of Systolic Blood Pressure in the VC Period	Safety
4.15.2.X	Box Plot of Diastolic Blood Pressure in the VC Period	Safety
4.15.3.X	Box Plot of Pulse in the VC Period	Safety

Figure No.	Title	Population
4.15.4.X	Box Plot of Respiratory Rate in the VC Period	Safety
4.15.5.X	Box Plot of Body Temperature in the VC Period	Safety

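### The protocol's coprimary subgroup by intertriginous involvement is missing from the SAP without a record, and the only visible intertriginous efficacy output averages over participants who had no involved region to clear.

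*SAP*

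**What the plan says.** **Coprimary subgroups.** Protocol 10.4.1 gives examples of baseline subgroup factors. The list ends with "prior cyclosporine therapy, and intertriginous involvement at baseline) will be performed", and details are left to the SAP. SAP 7.3.3 lists baseline EASI, age, sex, race, region, season and "Prior systemic or phototherapy (yes or no". It has no intertriginous item. SAP 11.1, which covers departures from the protocol, mentions only the rephrasing of endpoints and two revised population definitions. The flag itself is kept: SAP 6.1.2 summarizes "Intertriginous involvement at baseline (no/yes" as a baseline characteristic.

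**Count of involved regions.** Protocol 8.2.2.1 states: "The presence of AD lesions in the intertriginous regions (ie, axillae, anogenital area, inframammary folds, and infra-abdominal folds) will be determined at each visit". SAP Appendix A then plans Table 2.13.3, "Summary of By-Visit Change From Baseline in the Number of Intertriginous Regions With Active AD Involvement in the DB Treatment Period", and Figure 4.13.3, "Mean and Standard Error Plot of By-Visit Change From Baseline in the Number of Intertriginous Regions With Active AD Involvement". Both are labelled ITT. SAP 5.3.1 defines that population: "All participants who are randomized to the study constitute the ITT population". The inclusion criteria in Protocol 5.1 do not ask for any involved intertriginous region.

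**Purpose.** The Amendment 1 entry in Protocol Appendix C says that an exploratory endpoint was added to characterize efficacy in participants who have moderate AD with intertriginous involvement.

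**The concern.** Two separate matters bear on the same clinical question, namely how well the cream works in participants with disease in the folds.

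First, a subgroup analysis that the protocol says will be done has no counterpart in the SAP, and nothing explains why. A reader who compares the two documents after unblinding cannot tell whether it was dropped deliberately or overlooked.

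Second, the remaining output does not answer the question for the group named in the amendment rationale. A participant with no involved region at baseline can only stay at zero or rise. A small mean change in ITT could therefore mean that the cream does little in the folds, or only that few participants had fold disease.

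Together, these leave the visible plan without a direct efficacy estimate in participants with intertriginous involvement, either on EASI75 and IGA-TS or on the region count.

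**Working it through.** **Figures in the plan.** The documents give no effect size, SD or power for the intertriginous analysis. Their only power figures are for the six coprimary and key secondary endpoints (above 95% each). With 225 randomized 2:1 (150 and 75), Fisher exact power reproduces these. The lowest is ITCH4 on Day 2 (20% vs 3%), at 97.8%. None of them concerns this point.

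**Step 1: match the subgroup lists.**

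| Protocol 10.4.1 | SAP 7.3.3 |
|---|---|
| Geographic region | Present |
| Age | Present |
| Gender | Present (as sex) |
| Race | Present |
| Baseline EASI | Present |
| Season enrolled | Present |
| Prior cyclosporine | Within prior systemic or phototherapy |
| Intertriginous involvement | None |

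Seven of the eight protocol factors have a counterpart. The planned outputs agree with the seven-item list. Tables 2.1.4 to 2.1.10 and 2.2.4 to 2.2.10, and Figures 4.1.1.1 to 4.1.1.7 and 4.2.1.1 to 4.2.1.7, are four unbroken runs of seven. No gap in that numbering suggests that an intertriginous subgroup output was removed from the public copy.

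**Step 2: what the ITT mean difference estimates.** Let f be the share with at least one involved region at baseline, taken as equal in both arms (true in expectation under randomization). Let D be the difference in mean change, ruxolitinib minus vehicle, among involved participants. Let w_R and w_V be the mean numbers of newly involved regions among uninvolved participants. Then

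ITT difference = f × D + (1 − f) × (w_R − w_V).

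If uninvolved participants do not change, the second term is zero and the ITT difference is f × D. That is arithmetic. Only f and D must be assumed, because the documents give neither.

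**Step 3: illustration.** Assume mean changes of -0.8 (ruxolitinib) and -0.3 (vehicle) among involved participants, so D = -0.8 − (-0.3) = -0.50.

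| Assumed f | No new involvement: f × D | New involvement 5% on ruxolitinib, 10% on vehicle |
|---|---|---|
| 20% | -0.10 | -0.10 + 0.80 × (-0.05) = -0.14 |
| 30% | -0.15 | -0.15 + 0.70 × (-0.05) = -0.185 |
| 50% | -0.25 | -0.25 + 0.50 × (-0.05) = -0.275 |
| 70% | -0.35 | -0.35 + 0.30 × (-0.05) = -0.365 |

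The effect in involved participants is -0.50 in every row. What changes is the share of participants who could show it and, in the last column, a different effect: prevention of new involvement.

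**Step 4: size of the restricted group.** At f = 20% it has 0.20 × 150 = 30 and 0.20 × 75 = 15 participants. At f = 50% it has 75 and about 38. A restricted estimate is interpretable but may be imprecise.

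**The case against.** **ITT is a legitimate summary here.** New areas of AD are expected and treated in this trial (Protocol 4.1 and 6.1), and a count over everyone captures both clearance and spread. Randomization gives both arms the same expected share involved, and that share will be reported. This stands, and it is why the ITT version should stay. It does not supply the estimate in involved participants.

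**Text may be missing.** The public copy has no text under SAP 7.6.1, and Table 2.13.2 is absent from the numbering, so a restricted count analysis may exist out of sight. This limits the second matter to the visible plan. It does not alter the ITT label on Table 2.13.3 and Figure 4.13.3, or the list in SAP 7.3.3.

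**The protocol list is illustrative.** It gives examples and defers to the SAP. That permits a different list, but it does not explain why one named factor alone has no counterpart or why SAP 11.1 is silent.

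**Stronger readings to avoid.**

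- A reader might infer that power is lost. The documents do not support this. Table 2.13.3 is titled as a summary only, whereas its neighbour, Table 2.13.1, is "Summary and Analysis of Total %BSA Affected by AD in the DB Treatment Period". No test or alpha is assigned to the count, and Type I error control covers only the coprimary and key secondary endpoints. Any power figure would rest on assumed inputs, and its direction can reverse. At f = 20%, with the changes in Step 3 and an assumed SD of 0.9, nominal power is 42% in involved participants. In ITT it is 34% with no new involvement, but 47% with new involvement of 5% vs 10%.
- A reader might also infer that the SAP dropped prior cyclosporine. Protocol 5.1 lists cyclosporine among systemic treatments, so the broader prior-therapy subgroup covers it.
- Finally, the missing coprimary subgroup does not dilute Table 2.13.3, and restoring it would not change that table.

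**Conclusion.** Both matters hold, and they are separate. The first is an unrecorded difference between protocol and SAP: one named coprimary subgroup factor of eight has no counterpart, and SAP 11.1 does not say so. This rests on the text alone.

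The second is a limit on interpretation. The only visible intertriginous efficacy output reports f times the effect in involved participants when the uninvolved stay at zero, and otherwise a mixture of clearance and new involvement. The share f is not given. At an assumed 20% to 70%, an assumed effect of -0.50 regions would be shown as -0.10 to -0.35. The scaling by f is exact if the share is equal in both arms and uninvolved participants do not change. The values of f and of the effect are illustrations.

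This is an inexpensive improvement to exploratory and subgroup reporting. It does not touch the validity of the coprimary or key secondary analyses.

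**What to change.** 1. Add intertriginous involvement at baseline (yes or no) to SAP 7.3.3, with matching EASI75 and IGA-TS subgroup tables and figures and a row in each forest plot (Figures 4.1.2 and 4.2.8).
2. Keep Table 2.13.3 and Figure 4.13.3 in ITT, and repeat both in ITT participants with at least one involved region at baseline, showing the number of participants per arm at each visit.
3. Report, by arm and visit, the proportion with new involvement among participants who had none at baseline.
4. Note in SAP 11.1 that prior cyclosporine has been broadened to prior systemic or phototherapy. No other change is needed for that factor.

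The cost is a few lines of SAP wording and a small number of added outputs. The baseline flag and the by-visit region data are already collected, so no protocol procedure, visit or case report form changes. The additions are descriptive and need no alpha. They should be settled before the primary database lock, when the sponsor is unblinded.
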